## 9.0 Data Analysis

- We will conduct a thematic analysis to explore themes from individual phone interviews. Feasibility and acceptability will be assessed using descriptive and non-parametric statistics. Exploratory analyses will be conducted to assess for trends and effect sizes. [name] of the College of Nursing statistician will conduct all analyses. The apriori stated analysis is listed below.  
This is a pilot study for feasibility. For these pilot data we will emphasize descriptive statistics such as means, standard deviations, effect sizes, medians, interquartile ranges, frequencies, and percentages to demonstrate the feasibility of recruitment, adherence, and retention, treatment effects over time, and proof of concept. Our statistical approach for a full trial of these hypotheses will be Generalized Linear Mixed Models (GLMM) with an identity link function for a continuous outcome or a logit link function for a binary outcome. Conceptually, GLMM is a more advanced version of repeated measures ANOVA that can account for potential correlation among multiple measurements over time while having flexibility in fitting outcomes with different distributions (such as normal, binomial or Poisson, etc.). One advantage of this approach over repeated measures ANOVA is that there is no assumption that participants are measured at every, or even the same, time points. Therefore, these models are very flexible at handling missing data. Participants who have a missing observation are not excluded, thus, this produces the intention to treat (ITT) full information maximum likelihood (FIML) model. Conducting these models on pilot data help with sample size calculations for a future R01 submission.

## 10.0 Quality Control and Quality Assurance

Data will be continuously evaluated for protocol adherence during weekly meetings with the PIs and the study staff. [name] will evaluate all data for quality during weekly study meetings. Biweekly visits will be conducted by the PI to ensure that data collection is carried out according to the protocol.

## 11.0 Data and Safety Monitoring

Serious adverse events will be monitored and tracked at each follow-up period. Patients will be queried at the phone call and at 6 weeks if they have had any visits to the emergency department or hospitalizations (see attached checklist). We will also ask if they have had any symptoms of cardiac-related problems such as chest, arm or jaw pain while exercising or not exercising. Data will be recorded on an excel spreadsheet and reviewed by the PI at weekly study meetings. Any unanticipated adverse events or problems will be reported to the IRB within 7 days on notification. The PI will monitor safety data. Subjects are free to withdraw from the study at any time. If a subject withdraws from the study we will ask the subject (only once) if they are willing to come

back for the follow-up tests. If the subject does not want to complete the study, no further contact attempts will be conducted and the subject will be discontinued from the study (this will be reported at the annual continuing review).

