#### **Risk associated with the intervention.**

There are no known risks associated with activities to break up sedentary time as they are considered usual activities of daily living.

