### **Adverse Event and Serious Adverse Event Collection and Reporting**

Adverse events will be tracked on an ongoing basis for the full sample using an adapted version of the NIA Adverse Event Form (<https://www.nia.nih.gov/research/dgcr/clinical-research-study-investigators-toolbox/adverse-events>) and serious adverse events will be tracked using the NIH Serious Adverse Event Form

(<https://www.nia.nih.gov/research/dgcr/clinical-research-study-investigators-toolbox/adverse-events>). Adverse events will be reviewed during semi-annual meetings of the Data Safety Monitoring Committee (see 3.0 below for details). The PI will be informed of serious adverse events as soon as they occur and will notify the Safety Officer (Chair of the Committee) within 24 hours of notification. In addition, adverse events and serious adverse events will be reported to the UIC IRB and NIA consistent with their established protocols and will use the NIA AE/SAE Flow Process to guide this process and timeline (<https://www.nia.nih.gov/research/dgcr/clinical-research-study-investigators-toolbox/adverse-events>).

AEs will be defined as any health-related event that occurs within the intervention or assessment measure sessions. Expected AEs may include strained or sore muscles and fatigue. AE severity will be classified as:

- Mild - if the symptoms are tolerated and do not interfere with the participant's daily life.
- Moderate – if the symptoms cause some concern or some disruption to the participant's daily life, but can be alleviated through rest or relatively simple non-medical intervention.
- Severe – if the symptoms cause a major disruption in their daily life and require medical intervention or drug therapy.

All AEs will be documented using the Adverse Event Form by the PI. The PI will assess the relatedness of the AE to the study intervention and the expectedness of the AE. The PI will follow the Adverse Event flow chart to determine routing and reporting of the AE. All AEs will be reported to the DSMC and IRB in accordance with reporting guidelines.

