SAEs are not expected to occur within this intervention. However, potential SAEs could be a serious injury related to the intervention, a cardiac event resulting from physical activity, and death. All SAEs will be documented in the Serious Adverse Event form and reported to the NIA program officer and Safety Officer within 48 hours. All participant deaths will be reported to the NIA program officer and Safety Officer within 24 hours. All SAEs will be reported to the DSMC and IRB in accordance with reporting guidelines.

In addition to holding semi-annual DSMC meetings, all AE and SAE data will be reported quarterly by the pilot PI to the NIA project officer and Safety Officer.

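### The scheduled safety questions do not ask about the adverse events the plan expects, and no other active, scheduled way of finding non-serious events is described

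*Combined protocol and SAP*

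**What the plan says.** Section 11.0 opens with its purpose: "Serious adverse events will be monitored and tracked at each follow-up period". It then schedules the questions: "Patients will be queried at the phone call and at 6 weeks if they have had any visits to the emergency department or hospitalizations", with the pointer "see attached checklist". A further question follows: "We will also ask if they have had any symptoms of cardiac-related problems such as chest, arm or jaw pain while exercising or not exercising".

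The subsection on adverse event collection and reporting names what is anticipated: "Expected AEs may include strained or sore muscles and fatigue". For serious events it says that "potential SAEs could be a serious injury related to the intervention", and adds an activity-related cardiac event and death. It grades events as follows:

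- mild: tolerated, with no effect on daily life;
- moderate: some concern or disruption, relieved by rest or simple non-medical means;
- severe: major disruption that needs medical treatment.

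It commits to continuous tracking in all participants on an adapted NIA form, with the PI documenting each event. It defines an adverse event as one arising in the course of intervention or assessment sessions.

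Section 7.0 says of the intervention: "There are no known risks associated with activities to break up sedentary time". The section numbered 1.3 (protection against study risks) acknowledges a small risk of muscle soreness.

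Section 6.0 (study interaction 3) provides a phone interview after the intervention about difficulties and what worked.

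**The concern.** Safety and tolerability are part of whether a home activity program is feasible in adults up to 89. Adverse event data go to the Safety Officer and the NIA quarterly and to the monitoring committee twice a year, and the pilot is meant to inform a larger trial. A low count of soreness, strain or fatigue will be read as good tolerability. That reading is safe only if participants were asked.

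The questions described are aimed at events that lead to hospital or suggest heart disease. The expected events are of another kind. A form for recording events does not itself find them, and the text does not say who asks about non-serious events, in what words, when, or whether both arms are asked alike.

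**Working it through.** The plan states no figure on this point, so there is none to reproduce. The check is a comparison of text, followed by a short illustration.

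**1. Named events against the scheduled questions (section 11.0)**

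| Event the plan names | Class in the plan | Reached by the scheduled questions described? |
|---|---|---|
| Muscle strain or soreness | Expected AE | Not asked. The arm-pain item might catch some; a case leading to an emergency visit would be caught |
| Fatigue | Expected AE | Not asked |
| Serious injury | Potential SAE | Probably, through the emergency or hospital question |
| Cardiac event | Potential SAE | Yes, through the cardiac and hospital questions |

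The questions suit the serious events and ask directly about 0 of the 2 expected kinds. (Death, the third potential SAE, is not a matter for participant questioning.)

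**2. Severity grades.** By the plan's own wording, mild and moderate events need no medical care. They would not normally produce an emergency visit or a hospital stay.

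**3. Timing.** "Patients will be queried at the phone call and at 6 weeks if they have had any visits to the emergency department or hospitalizations" does not identify the call. Section 6.0 describes several possibilities:

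- The baseline call and the call giving the allocation both precede the intervention. If either is meant, the 6-week query is the only scheduled one that covers the intervention period, with recall of 6 weeks or more.
- The device set-up call is described for the intervention arm only. If that is meant, controls have no counterpart.
- The follow-up interview comes after 6 weeks, 8 days of monitor wear and return mailing: 42 + 8 = 50 days from the start, plus postage.

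**4. Contact by arm.** Sections 6.0 and 13.2 describe a set-up call, app prompts, requests for feedback and text messages for the intervention arm. Controls are told their allocation and sent guidelines. No contact with controls during the 6 weeks is described.

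**5. Illustration of what incomplete capture does.** Arm size n = 40 is from section 4.0. The true risk p and the captured share c are assumptions; the documents give neither. Expected recorded count = 40 × p × c. Chance of recording at least one = 1 − (1 − p × c)^40.

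| p | c | Expected count | Chance of at least one |
|---|---|---|---|
| 5% | 100% | 2.0 | 87.1% |
| 5% | 50% | 1.0 | 63.7% |
| 5% | 25% | 0.5 | 39.5% |
| 20% | 100% | 8.0 | >99.9% |
| 20% | 50% | 4.0 | 98.5% |
| 20% | 25% | 2.0 | 87.1% |

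With zero events recorded in 40, the one-sided 95% upper bound on the recorded risk is 1 − 0.05^(1/40) = 7.2%. This bounds the true risk only if c = 1. At c = 50% the bound on the true risk is 0.0722 / 0.5 = 14.4%, and at c = 25% it is 0.0722 / 0.25 = 28.9%. Without an elicitation method, c is unknown and so is the bound.

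**6. Statements that do not agree.** Section 7.0 ("There are no known risks associated with activities to break up sedentary time") stands against the soreness risk in section 1.3 and the expected and potential events in section 11.0. The session-based definition of an adverse event also fits poorly with a program that runs through the day at home, and with a control arm that has no intervention sessions.

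**The case against.** The best defense is that the quoted questions are an SAE screen and are labeled as such. Non-serious events belong to the next subsection, which promises continuous tracking of everyone, grading, and assessment of relatedness and expectedness. The wording of a question is an operational detail that may well be in the attached checklist or the adverse event form, neither of which is in the public text. The follow-up interview and the week-6 review of app data with participants (section 8.0) also invite remarks about soreness or tiredness. The suggested activities are very light, and no comparison of adverse events between arms is planned.

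Much of this stands, and it rules out stronger readings. A reader might infer that the plan misses all of its expected events, or that mild and moderate events can come to light only when volunteered. The documents do not support that: the checklist and form may hold further items, the interview may bring events up, and a severe strain or serious injury would probably reach the emergency or hospital question. A reader might also infer that reports will be inflated in the intervention arm. No route for reporting adverse events through the app is described, so this is a possibility only.

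What does not stand is that the tracking promise closes the gap. It says where events are written down and leaves open how they are found. The interview is not described as a safety assessment and comes late for minor, passing symptoms.

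**Conclusion.** The concern holds in a limited form. As written, the plan describes no active, scheduled elicitation of the non-serious events it expects, so mild and moderate events are likely to be under-counted, possibly to a different degree in the two arms. How far cannot be computed: the event rate and the captured share are both unknown, and the figures above show only the effect of assumed values.

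The conclusion rests on the visible text. If the attached checklist already asks about strain, soreness, fatigue and injury in both arms, what remains is to say so in section 11.0, identify the call, and reconcile the definition and the risk statements. This is a worthwhile, inexpensive improvement to safety ascertainment. It does not threaten the feasibility aims.

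**What to change.** In section 11.0:

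- Unless the attached checklist already has them, add fixed yes/no questions on muscle strain or soreness, fatigue, and falls or other injury since the last contact.
- Ask them in identical words at the same contacts in both arms, before the interview about the program begins.
- State which call is meant by the phone call, so that it is clear which queries fall after randomization, with at least one common to both arms.
- Reconcile the session-based adverse event definition with ascertainment at home in two arms, so that an event reported by a control or between contacts has a clear status.
- Reconcile the risk statement in section 7.0 with those in sections 1.3 and 11.0.

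The cost is a few minutes per contact and more minor events to record, grade and report. Treatment, eligibility and sample size are unaffected.

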### **6.0 Study Design and Procedures**

This research will be performed via telephone/video conference to maximize social distancing and participant safety. The intervention will be performed by the participants at home.

This is a pilot randomized, controlled trial of a 6-week intervention for feasibility. Outcome measures will be obtained at baseline and at 6-weeks. Behavior choices and preference data will be continuously captured during the intervention. We will randomize 80 older Latinos from the Chicago Latino community to either an ecological momentary intervention using fitbits (n=40) or to physical activity guidelines (n=40).

Study interaction 1-baseline test (Approximately 2 hours). Participants will be screened for inclusion/exclusion criteria. If criteria for inclusion in the study are met participants will undergo informed consent process. Following informed e-consent conducted via zoom video/telephone participants will be asked about their demographics (demographic

form), and contact information (Face sheet), and then they will be asked about their medical history. Following the medical history we will fill out the Charlson co-morbidity questionnaire, and conduct the following cognitive function measures as approved by the NIH for use via video call: a. Picture vocabulary test, b. Picture sequence test, c. List sorting test, d. Oral reading recognition test, e. Auditory verbal learning test, and the Trail Making test A and B. Following the cognitive function testing, we will conduct a phone/video interview. The interview will be recorded, analyzed and used to develop the intervention.

Following the interview we will conclude the phone call and send the participants an activity monitor to be worn on the waist for 8 days to measure sedentary time: The participants will mail the monitor back to us after 8 days. Once we have received the physical activity monitor we will randomize the participant to intervention or control.

**Optional in-person visit (approximately 1 hour) If the participant is willing and able to undergo an MRI scan. No contrast will be used.**

- The MRI Visit will take place about one-week after the initial phone call. Participants will come to the Magnetic Resonance Imaging Center, 3T research center [name] and return the actigraph to us. We will ask participants to do the following:

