real-time feedback on activity options selected and how successful they were in adopting the option. These data will allow us to track underlying preferences for behaviors and tailor the program accordingly. Participants will receive a message immediately with positive choices for behavioral action. Resulting actions and delivery of the intervention will be automatically captured and downloaded in real time. We will teach them how to use these devices once they are assigned to the intervention group. The sensor and activity tracker will record their everyday physical activity level. When participant stays sedentary too long during a day, the smartphone app will send a real-time reminder with some physical activity options for participant to choose designed based on their preferences and focus group discussions (e.g., standing up 5 times, taking 20 steps, or performing a short dance routine). Resulting actions and delivery of the intervention will be automatically captured and downloaded into the devices in real time.

Participants randomized to the control group will be sent general guidelines for disruption of sedentary time.

Study interaction 3-Follow-up (Approximately 1 hour): At the completion of the 6-week intervention period all participants will be sent an activity monitor to be worn on the waist for 8 days to measure sedentary time: The participants will mail the monitor back to us after 8 days. Once we have received the physical activity monitor we will schedule a phone interview with the participants to understand where they had difficulty and what did or did not work for them. We will then repeat the cognitive function tests and the optional MRI scan.

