- **Image Analyses** DTI: FSL with TBSS, we will quantify FA and MD from whole brain and tract specific white matter. T1/FSPGR: Using FreeSurfer, we will extract hippocampal volumes (right and left) as well as sub-fields of the hippocampus adjusted for intracranial volume. T2-FLAIR: Using standard software, we will quantify white matter hyperintensity volumes across the entire brain white matter. We will use a seed-based approach to measure resting state networks of interest. *Functional connectivity networks*: Functional brain networks will be generated using the resting-state fMRI toolbox, CONN (<http://www.nitrc.org/projects/conn>; (Whitfield-Gabrieli and Nieto-Castanon, 2012)). In brief, raw EPI images are realigned, co-registered, normalized, and smoothed before analysis. Any confound effects from motion artifact, white matter, and CSF are regressed out of the signal. Using the same label maps as the structural brain networks, functional brain networks will be derived using pairwise BOLD signal correlations.

- **Feasibility and acceptability:** We will conduct formative assessments at the completion of the intervention at week 6. We will derive the number of times the phone app was accessed and the number and types of behavior choices that were made. We will review these data with participants in order to understand where they had difficulty and what did or did not work for them.

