### **Content of Data and Safety Monitoring Report/ SO Reports.**

The content of the SO report will include study status/quality, participant descriptive information, adverse events, and dropout rates/reasons.

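### The withdrawal rule makes one undivided request to return for testing and has no step for asking why, so interview-based acceptability (Aim 3) will come mainly from completers

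*Combined protocol and SAP*

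**What the plan says.** Section 11.0 (Data and Safety Monitoring) sets the rule: "If a subject withdraws from the study we will ask the subject (only once) if they are willing to come", continuing "back for the follow-up tests. If the subject does not want to complete the study, no further contact attempts will be conducted". The subject is then discontinued.

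Section 6.0 describes the conduct of the trial: "This research will be performed via telephone/video conference to maximize social distancing and participant safety". Consent, cognitive tests and interviews are by telephone or video, and the waist-worn monitor goes out and comes back by mail. Only the optional MRI visit, with its added NIH Toolbox tests, needs attendance.

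Follow-up is a chain (Section 6.0, Study interaction 3). After the 6-week period all participants are sent the monitor. Then: "Once we have received the physical activity monitor we will schedule a phone interview with the participants to understand where they had difficulty". The cognitive tests and the optional MRI come after that. Section 8.0, under feasibility and acceptability, gives the same timing: "We will conduct formative assessments at the completion of the intervention at week 6". It also names a second source: "We will derive the number of times the phone app was accessed and the number and types of behavior choices that were made".

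The content of the Safety Officer report, listed under Section 11.0, includes "adverse events, and dropout rates/reasons". Section 3.0 makes feasibility and acceptability of the EMI the subject of Aim 3, and Section 4.0 gives 40 participants per arm.

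**The concern.** Aim 3 asks whether older Latinos can and will use the EMI. Its burden is specific: a Fitbit that buzzes after more than 10 minutes without activity, app suggestions, and reminders to enter feedback. Controls are sent guidelines. Anyone who leaves because of that burden has the most to say about acceptability.

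Followed as written, the rule spends the one permitted request on a return for testing. It does not mention the interview, does not offer the monitor or the telephone tests as separate choices, and does not say that a person may stop the EMI and stay in follow-up. Nor does it say when the reason for leaving is asked, although that reason has to be reported. Someone who would have given five minutes on the telephone, but not the full follow-up, has no planned way to do so. The interview account of what worked would then come largely from people for whom the EMI was tolerable.

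**Working it through.** The plan states no dropout rate, acceptability threshold or derivation of the sample size, so there is no figure to reproduce. The point rests first on reading the sections together.

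**Reading**

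1. *Mode.* Section 6.0 is remote except for the MRI visit; the Section 11.0 request speaks of coming back. The wording does not fit the design, whatever staff take it to mean.
2. *Content.* The request covers tests. The interview is a separate item in Section 6.0 and is not named in the request.
3. *Sequence.* Interview and cognitive tests both wait for the monitor to be returned. Unless they are offered separately, declining the monitor closes off the rest.
4. *Reasons.* The report must contain dropout reasons. Section 11.0 describes the contact at withdrawal and gives no step for asking them.
5. *What is already held.* Section 6.0 has actions and delivery captured automatically in real time, and EMI participants enter feedback on the options they chose and how well these worked. Section 8.0 counts app accesses and choices towards feasibility and acceptability. These data exist up to the point of withdrawal.

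So the gap is in the interview, the stated reasons and partial follow-up, and not in all acceptability data.

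**Illustration of size**

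From the plan: n = 40 in the EMI arm. Assumed: the withdrawal rate, 80% acceptability among completers, and no answer from any withdrawer. With q withdrawers and a completers who find the EMI acceptable, the all-randomised figure lies between a/40 (no withdrawer agrees) and (a + q)/40 (all agree). The width is q/40.

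For q = 8: a = 0.80 × 32 = 25.6. Lower bound 25.6/40 = 64%; upper bound (25.6 + 8)/40 = 33.6/40 = 84%.

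With a rounded to whole people:

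| Withdrawal | q | Completers | a | Completer figure | All 40: bounds | Width (points) |
|---|---|---|---|---|---|---|
| 5% | 2 | 38 | 30 | 79% | 75% to 80% | 5 |
| 10% | 4 | 36 | 29 | 81% | 72.5% to 82.5% | 10 |
| 20% | 8 | 32 | 26 | 81% | 65% to 85% | 20 |
| 30% | 12 | 28 | 22 | 79% | 55% to 85% | 30 |

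The completer figure stays near 80% throughout and does not reveal the widening range. If half of the withdrawers answered a short question, the width would halve: 10 to 5 points at 10% withdrawal, 20 to 10 at 20%, 30 to 15 at 30%.

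**Between-arm outcomes**

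Assume 20% loss in EMI, 5% in control, and lost participants scoring d SD worse than completers in their own arm. The completer difference is then biased by d × (0.20 − 0.05): 0.045 SD at d = 0.3 and 0.075 SD at d = 0.5. With 32 and 38 completers the standard error is √(1/32 + 1/38) = 0.24 SD, so the bias is about 0.2 to 0.3 of one standard error.

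**The case against.** The other side has good points, and they limit the concern.

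- A reader might infer that the outcomes and views of those who quit are simply lost, and that acceptability rests on completers alone. The documents do not support this. Those who say yes are followed up, and app use, choices and feedback up to withdrawal are held. Counts show that use stopped but not why, however, and Section 8.0 itself plans to go over these data with participants to find out where they had difficulty.
- A reader might also infer that asking only once is the flaw. It is not: it protects the right to withdraw. The weakness is in what the one contact asks.
- *Come back* need not mean attendance, and nothing in Section 11.0 forbids partial acceptance. Sensible staff could read it broadly. That leaves the matter to the individual caller, which is a reason to write it down.
- Leaving is not the only escape from prompts: under Section 13.2 a reply of STOP ends reminders and text messages. The text does not extend this to the Fitbit buzz.
- Listing dropout reasons in the report shows that they are meant to be collected. The telephone script, interview guide and satisfaction survey are named as appendices, but their content is not in the text available, so they may contain a suitable item. It cannot be said either way whether withdrawers receive the survey.
- Sections 9.0 and 12.0 say that mixed models keep participants with a missing observation. That is presented as the approach for a full trial, while the pilot emphasises descriptive statistics. With two assessments, a person lost before follow-up contributes only baseline, and no model supplies interview answers that were never sought.
- A reader might infer a material bias in the comparison of arms. Unequal dropout is plausible but nowhere stated, and under the assumptions above the bias is small beside its standard error, on cognitive outcomes labelled exploratory.

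**Conclusion.** The point holds in a limited form. The withdrawal rule makes a single undivided request, does not distinguish stopping the EMI from leaving follow-up, and is not connected to the reporting of dropout reasons. Given where the interview falls, interview-based acceptability will come mainly from completers, while the app and feedback data still cover withdrawers up to the day they leave.

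The size is unknown. The range of 64% to 84% assumes 8 withdrawals among 40, 80% acceptability among completers, a yes/no acceptability measure that the text does not define, and silence from every withdrawer. The 64% is the worst case, not an expected value. The case rests on Aim 3 and not on bias in the outcome comparison. It is a worthwhile, inexpensive improvement and does not undermine the design.

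**What to change.** Keep the single contact in Section 11.0 and change its content, in the protocol and in the telephone script. In that call, with each item open to refusal:

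1. ask the reason for leaving and record it for the Safety Officer report;
2. offer a few brief acceptability questions;
3. offer the telephone or video cognitive tests and the mailed monitor as separate choices, neither dependent on the other.

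Replace the *come back* wording with *complete by telephone, video or mail*. State that a participant who stops the EMI but remains in follow-up has not withdrawn from the study.

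In Sections 9.0 and 12.0, say that interview or survey acceptability is reported for all randomised to EMI, with non-responders as a separate category and best-case and worst-case bounds beside the responder figure. This settles how those who still decline are counted.

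The cost is some wording, a line in a table, and a slightly longer call for someone who is leaving the study.
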